### ***3.7.1 Imputation of Missing/Partial Dates***

#### ***3.7.1.1 Adverse Events***

For AEs, the following imputation rules will be applied to impute start dates under conservative principles:

- If year, month and day are all missing then assign the date of first dose of Study Drug
- If month and day are missing and year is:
  - the same as the year of the first dose of Study Drug then assign the month-day of first Study Drug
  - earlier than the year of the first dose of Study Drug then assign December 31
  - after the year of the first dose of Study Drug then assign January 1
- If only day is missing and month-year is:
  - the same as the month-year of the first dose of Study Drug then assign the day of first Study Drug
  - earlier than the month-year of the first dose of Study Drug then assign the last day of the month
  - after the month-year of the first dose of Study Drug then assign the first day of the month

Imputation will be performed only for the end date only if the day or month is missing (i.e., year is present) for a resolved AE as follows:

- If month and day are missing and year is
  - the same as the year of the last dose of Study Drug then assign the month-day of the last dose of Study Drug
  - otherwise, assign December 31
- If only day is missing then assign the last day of the month

If the imputed start date is later than the imputed end date then set the imputed start date to the imputed end date.

Analysis period will be assigned by comparing the imputed AE start date with the period start/end date.

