#### ***3.7.1.2 Prior/Concomitant Medications***

For prior/concomitant medications, the following imputation rules will be applied to impute start dates under conservative principles:

- If year, month and day are all missing then assign the date of first dose of Study Drug

- If month and day are missing and year is:
  - earlier than the year of the first dose of Study Drug then assign December 31
  - otherwise, assign January 1
- If only day is missing and month-year is:
  - earlier than the month-year of the first dose of Study Drug then assign the first day of the month
  - otherwise, assign the last day of the month

Imputation will be performed only for the end date only if the day or month is missing (i.e., year is present) for a stopped prior/concomitant medication as follows:

- If month and day are missing then assign December 31
- If only day is missing then assign the last day of the month

If the imputed start date is later than the imputed end date then set the imputed start date to the imputed end date.

Analysis period will be assigned by comparing the imputed medication start/end date with the period start/end date.

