- TEAEs potentially related to Study Drug. Related is defined as “Related”, “Possible”, or missing relationship to Study Drug
- Any treatment-emergent adverse event by severity. At each level of patient summarization, a patient with multiple events is counted only once according to the worst reported severity. Adverse events with missing severity will be categorized as “Missing” for this summary.
- TEAEs potentially related to Study Drug by severity
- Serious TEAEs
- Serious TEAEs potentially related to Study Drug
- TEAEs leading to permanent treatment discontinuation
- TEAEs leading to death.

Adverse event summaries will be presented by descending frequency of the percentage of patients in the Total column. An overview of AEs will be provided for all TEAEs. Treatment-emergent AEs, treatment-emergent SAEs, TEAEs that lead to treatment discontinuation, and TEAEs leading to death will be listed. Note that imputed dates will be used for defining TEAEs and classification of TEAEs into analysis periods. Originally reported dates will be used for listings.

For AEs occurred during Randomized Treatment Post-Treatment Period, the frequency of patients and number of events of any TEAEs, Serious TEAE will be summarized by MedDRA preferred term and system organ class.

In addition, an overview of adjudicated AEs will be provided for pancreatitis and MACE separately. Adjudicated events will also be listed.

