### **3.7.2.2 *Flu-Like Reactions***

Flu-like reactions (FLRs) will also be summarized by analysis period, treatment group and overall using the MedDRA coding system, by system organ class and preferred term. Number and percent of patients reporting at least one FLR will be summarized also.

Flu-like reactions are defined as AEs with following preferred term or verbatim: flu-like illness, chills, myalgia, arthralgia, pyrexia, feeling hot, or body temperature increased, starting on the day of injection or the next day.

Percentage of injections leading to flu-like reactions will be summarized by analysis period, treatment group, and overall using descriptive statistics.

Percentage of the injections leading to flu-like reactions will be calculated as follows for each patient:  $(A/B) * 100$ , where A = number of injections leading to flu-like reactions, and B = total number of injections.

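### The AE end-date rule can move a follow-up event's start back to the last-dose day and into the Randomized Treatment Period (patients not entering the OLE, year-only end date)

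*SAP*

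**What the plan says.** SAP 3.7.1.1 imputes the end of a resolved AE in three ways.

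- Month and day missing, and the year is "the same as the year of the last dose of Study Drug then assign the month-day of the last dose of Study Drug".
- Month and day missing, any other year: "otherwise, assign December 31".
- Day alone missing: "If only day is missing then assign the last day of the month".

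A conflict rule follows: "If the imputed start date is later than the imputed end date then set the imputed start date to the imputed end date". The section closes by assigning the analysis period from the imputed AE start date. SAP 3.7.2 confirms that "imputed dates will be used for defining TEAEs and classification of TEAEs into analysis periods", and that listings show the dates originally reported.

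The period limits are in the safety analysis period table of SAP 3.7. For a patient who does not enter the OLE, the Randomized Treatment Period ends one dose interval after the last dose (7 days weekly, 14 days bi-weekly), and follow-up begins the next day. For OLE patients, treatment and follow-up form one combined period.

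The parallel rule for medications in SAP 3.7.1.2 is different: "If month and day are missing then assign December 31".

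**The concern.** The end-date rule does not look at when the AE began. An event that started after the last dose can therefore receive an end before its own start. The conflict rule then changes the start, which is the better-known of the two dates, to fit an end that was only guessed. The period is read from the changed start.

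The placebo-controlled safety tables could then contain events that were reported as starting in follow-up. The two periods are also summarised differently. SAP 3.7.2 gives randomized-period follow-up only any-TEAE and serious-TEAE tables. The Randomized Treatment Period also has tables by relatedness, by severity, and for events leading to discontinuation or death. A moved event can enter those tables.

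**Working it through.** The plan states no figure to reproduce, so the check applies its rules to dates.

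**Example (made-up dates).** The patient is dosed weekly, does not enter the OLE, and has a first dose on 4 July 2016 and a last dose on 26 June 2017. Those dates are 357 days apart, or 51 weeks, so the last dose is the Week 52 dose.

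- Randomized Treatment Period ends 26 June + 7 days = 3 July 2017.
- Follow-up starts 4 July 2017. Thirteen weeks (91 days) after the last dose is 25 September 2017.

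The broad reading of the conflict rule applies it to every start. The narrow reading applies it only to starts that were themselves imputed.

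| Reported start | Reported end | Imputed end | Start before → after reset | Period before → after |
|---|---|---|---|---|
| Aug 2017 (either reading) | 2017 | 26 Jun 2017 | 1 Aug → 26 Jun | Follow-up → Randomized Treatment |
| 15 Aug 2017 (broad) | 2017 | 26 Jun 2017 | 15 Aug → 26 Jun | Follow-up → Randomized Treatment |
| 15 Aug 2017 (narrow) | 2017 | 26 Jun 2017 | unchanged | Follow-up; end is 50 days before start |
| 1 Jul 2017 (broad) | 2017 | 26 Jun 2017 | 1 Jul → 26 Jun | Randomized Treatment throughout |
| 6 Jul 2017, bi-weekly (broad) | 2017 | 26 Jun 2017 | 6 Jul → 26 Jun | Randomized Treatment throughout (limit 10 Jul) |
| 15 Aug 2017 | 2018 | 31 Dec 2018 | unchanged | Follow-up |
| 15 Aug 2017 | Sep 2017 | 30 Sep 2017 | unchanged | Follow-up |
| 2017 only | 2017 | 26 Jun 2017 | 1 Jan, unchanged | Randomized Treatment throughout |

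Four conditions must therefore hold together for the period to change:

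1. The end has only a year.
2. That year is the last-dose year.
3. The patient does not enter the OLE.
4. The start, after the SAP's own start imputation, is more than one dose interval after the last dose.

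A day-missing start in the last-dose month fails condition 4. The start rule already sets it to the first of that month (or to the first-dose day, if that is the same month), on or before the last dose. In the last table row the start rule, not the reset, places the event on treatment.

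**How often condition 2 could hold.** Assume last doses fall evenly over a 365-day year. An event starting k days after the last dose then falls in the next calendar year with probability k/365.

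- Weekly, days 8 to 91: mean k = (8 + 91)/2 = 49.5, so the start falls in the last-dose year in 1 − 49.5/365 = 86%.
- Bi-weekly, days 15 to 91: mean k = 53, so 1 − 53/365 = 85%.
- The end must also fall in that year. With an assumed 14-day duration and weekly dosing, 1 − 63.5/365 = 83%.

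These are shares of follow-up AEs that already have a year-only end. They describe exact start days, so as a rate of moved events they need the broad reading. They are not expected counts.

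**Treatment-emergent status.** SAP 3.7.2 defines it by onset or worsening on or after first dose, with no upper limit. The reset date is the last dose, so the status does not change.

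**The case against.** The strongest reply is that this hardly ever happens. Follow-up lasts 13 weeks with 7 visits (Protocol 6.1.3). SAP 2.5.1 describes edit checks that prompt for missing data, with lock only after queries are resolved. A resolved event in that window whose end month is unknown should be rare. That stands, and it limits the severity.

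The second reply is that the reset names only the imputed start date, in a section about missing and partial dates. Elsewhere (SAP 3.7.2) the SAP puts the word imputed in brackets when it means reported and imputed starts alike. On that reading a complete start keeps its period. Against it, the period-assignment sentence uses the unbracketed term for every AE. The point is ambiguous, so a reader should not infer that complete starts are certainly overwritten. The narrow reading still leaves such records with an end before their start, and it still moves a start recorded as August 2017 into June.

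A third reply is that pulling events towards treatment is conservative. The SAP uses that word for filling in missing start dates, whereas here a known month is overridden because the end is vague. The rule acts in both arms, so a moved placebo event raises the comparator. No direction of bias is shown.

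A reader might also infer that flu-like reactions will be over-counted, because their definition requires an event "starting on the day of injection or the next day" and the reset date is an injection day. The SAP names imputed dates for defining TEAEs and assigning periods. It does not say they drive the flu-like timing test. If they do, such an event could be counted there, in OLE patients too. That remains conditional.

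**Conclusion.** The rule is wrong as written, and the error is minor. Under the four conditions above, a follow-up AE with a known start month and missing day is placed in the Randomized Treatment Period summary, against its reported month. With a complete start, it is either moved too or left with an impossible pair of dates.

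A reader might conclude that about four in five follow-up events with year-only ends would be moved. The documents do not support that as a finding. It needs evenly spread last doses, weekly dosing, a 14-day duration and the broad reading, and the number of year-only end dates is not given. Nor is the problem confined to patients who stop early: a Week 52 completer who does not enter the OLE goes to the same follow-up.

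OLE patients do not change period, because their treatment and follow-up are pooled. Efficacy is unaffected. Listings keep the reported dates, so a moved event can be traced, but the summary table would still be wrong.

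**What to change.** Amend two sentences in SAP 3.7.1.1.

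1. End date: an imputed AE end may not precede the reported or imputed AE start. For example, when month and day are missing, use 31 December of the recorded year or the end of the patient's follow-up, whichever is earlier, but never before the start.
2. Reset: apply it only to starts that are wholly or partly missing, and never move a start outside its reported month or year.

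In the example, the end for the August 2017 event becomes the earlier of 31 December and 25 September 2017, that is 25 September. The start stays at 1 August and the event remains in follow-up.

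While editing, state in SAP 3.7.2.2 whether the flu-like timing test uses reported or imputed starts.

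The cost is a short text change and a small programming change. No new data are needed and patients are not affected.

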#### ***3.7.1.2 Prior/Concomitant Medications***

For prior/concomitant medications, the following imputation rules will be applied to impute start dates under conservative principles:

- If year, month and day are all missing then assign the date of first dose of Study Drug

- If month and day are missing and year is:
  - earlier than the year of the first dose of Study Drug then assign December 31
  - otherwise, assign January 1
- If only day is missing and month-year is:
  - earlier than the month-year of the first dose of Study Drug then assign the first day of the month
  - otherwise, assign the last day of the month

Imputation will be performed only for the end date only if the day or month is missing (i.e., year is present) for a stopped prior/concomitant medication as follows:

- If month and day are missing then assign December 31
- If only day is missing then assign the last day of the month

If the imputed start date is later than the imputed end date then set the imputed start date to the imputed end date.

Analysis period will be assigned by comparing the imputed medication start/end date with the period start/end date.

### **3.7.2 Adverse Events**

All adverse events will be coded by the MedDRA dictionary version 19.1. Missing or partial dates will be imputed as outlined in Section 3.7.1. A treatment-emergent adverse event (TEAE) is defined as any event starting or getting worse on or after the first dose of Study Drug.

TEAE will be identified as follows based on the (imputed) AE start dates:

Case 1: If there is no “Formlink” link, and the AE (start date/time) occurs on or after the patient’s first dosing date/time, then the AE is treatment-emergent. Otherwise, if the AE (start date/time) occurs prior to the patient’s first dosing date/time, then the AE is not treatment-emergent.

Case 2: If there is a “Formlink” link between 2 AE records, then the 2 AE records will be chronologically ordered by AE start date/time and will be referred to as the “first” and the “second” AE respectively. AE severity (mild/moderate/severe) will then be compared pairwise.

Case 2a: The first AE record in the pair occurs before first dosing, and the second record occurs on/after dosing.

If the AE severity on the second record is worse than the severity on the first record or the severity on the second record becomes Serious AE, then only count the second AE as treatment-emergent. But, if the severity doesn’t worsen (i.e., the second record severity is the same or less severe than the first record severity) or doesn’t become SAE, then neither record is counted as treatment-emergent.

Case 2b: Both AE records in the pair occur on/after first dosing.

If the AE severity on the second record is worse than the severity on the first record or the severity on the second record becomes SAE, then count both records as treatment-emergent. But, if the severity doesn't worsen or doesn't become SAE, then only count the first record as treatment-emergent.

Case 2c: Both AE records in the pair occur before first dosing.

Neither AE is counted as treatment-emergent.

When counting the total number of treatment-emergent events, events linked together through change in severity will still be counted as separate events.

For AEs occurred during the Randomized Treatment Period, and the Combined OLE and OLE Post-Treatment Period , the frequency of patients with any incidence of AEs and the number of events will be summarized by analysis period, MedDRA preferred term and system organ class for:

- Any TEAE
- TEAEs potentially related to Study Drug. Related is defined as “Related”, “Possible”, or missing relationship to Study Drug
- Any treatment-emergent adverse event by severity. At each level of patient summarization, a patient with multiple events is counted only once according to the worst reported severity. Adverse events with missing severity will be categorized as “Missing” for this summary.
- TEAEs potentially related to Study Drug by severity
- Serious TEAEs
- Serious TEAEs potentially related to Study Drug
- TEAEs leading to permanent treatment discontinuation
- TEAEs leading to death.

Adverse event summaries will be presented by descending frequency of the percentage of patients in the Total column. An overview of AEs will be provided for all TEAEs. Treatment-emergent AEs, treatment-emergent SAEs, TEAEs that lead to treatment discontinuation, and TEAEs leading to death will be listed. Note that imputed dates will be used for defining TEAEs and classification of TEAEs into analysis periods. Originally reported dates will be used for listings.

For AEs occurred during Randomized Treatment Post-Treatment Period, the frequency of patients and number of events of any TEAEs, Serious TEAE will be summarized by MedDRA preferred term and system organ class.

In addition, an overview of adjudicated AEs will be provided for pancreatitis and MACE separately. Adjudicated events will also be listed.

### **3.7.2.1 *Injection site reaction (ISR)***

Injection site reaction (ISR) at injection site will also be summarized by treatment group and overall using the MedDRA coding system, by analysis period, system organ class and preferred term. Number and percent of patients reporting at least one ISR will be summarized also.

ISR is defined as any AE with MedDRA preferred term or verbatim that contains “INJECTION SITE”, that starts on the day of injection and persist for at least 2 days, or start any time and persist for at least 2 days, AE resolution date – AE start date + 1 day should be great than two days. AE with preferred term or verbatim that contains “INJECTION SITE” and missing resolution date will also be included.

Percentage of injections leading to Injection Site Reaction will be summarized by treatment group and overall using descriptive statistics.

Percentage of injections leading to Injection Site Reaction will be calculated as follows for each patient:  $(A/B) * 100$ , where A = number of injections leading to Injection site reaction (ISR), and B = total number of injections.

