The most frequently observed AEs with ISIS 304801 were local reactions at the injection site. Local cutaneous reactions at the injection site (LCRIS) defined as those events presenting as either pain, tenderness, erythema, pruritus or swelling occurring on the day of injection and persisting for at least 2 days were infrequent (~15% of injections), were almost always mild, resolved spontaneously, were non-progressive, and were not associated with systemic sequelae.

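### The injection site reaction (ISR) definition in SAP 3.7.2.1 says 2 days or more in words but 3 calendar days or more by formula, so reactions resolving the day after onset drop out of the ISR-specific outputs

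*SAP*

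**What the plan says.** SAP 3.7.2.1 selects adverse events whose preferred term or verbatim mentions the injection site and then applies a duration test. The words are "that starts on the day of injection and persist for at least 2 days, or start any time and persist for at least 2 days". The same sentence continues with a calculation, resolution date minus start date plus 1 day, and says that the result "should be great than two days". An injection site event with no end date passes without any test, because those with a preferred term or verbatim match "and missing resolution date will also be included".

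Three outputs rest on this definition: the ISR summary by system organ class and preferred term, the number and percent of patients with at least one ISR, and a per-patient percentage (A/B) × 100 in which "A = number of injections leading to Injection site reaction (ISR), and B = total number of injections".

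Two other places bear on the point. Protocol 10.6.2 plans a summary of injection site adverse events by group, preferred term and severity, and states no minimum duration. SAP 3.8, which lists departures from the protocol, does not mention a duration limit.

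**The concern.** The words and the formula in one sentence classify the same event differently. Duration does most of the work in this definition: the second limb of the wording accepts any onset time, so it contains the first limb, and what remains is a term match plus a duration cut. The placing of that cut decides which events count.

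Protocol 2.3.4 names local injection site reactions as the adverse events seen most often with the drug, so readers will look for the dedicated ISR outputs. Two programmers working from the same sentence could produce different patient percentages and different per-injection percentages. The treatment of missing dates adds an imbalance: a reaction documented as resolving the next day is left out, while one whose end was never recorded is counted.

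**Working it through.** **Inputs**

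- Rule in words: duration of 2 days or more (SAP 3.7.2.1).
- Rule as formula: D = resolution date − start date + 1, with D > 2 required (SAP 3.7.2.1).
- Day-count convention elsewhere: SAP 3.7.5 computes treatment duration as last day minus first day plus one, which is also an inclusive count.

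The plan states no figure to reproduce, so the check is to run each possible gap between start and resolution through the rules. For whole dates, D > 2 is the same as D ≥ 3. The last column gives the other possible reading of the words, elapsed time (resolution − start ≥ 2).

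| Resolution − start (days) | D (inclusive days) | Formula, D > 2 | Words on the inclusive count, D ≥ 2 | Words as elapsed time |
|---|---|---|---|---|
| 0 | 1 | no | no | no |
| 1 | 2 | **no** | **yes** | no |
| 2 | 3 | yes | yes | yes |
| 3 | 4 | yes | yes | yes |
| 4 | 5 | yes | yes | yes |

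On the formula's own count, the rules part at one point only. For start day d and resolution day d + 1, D = (d + 1) − d + 1 = 2, which satisfies 2 ≥ 2 and fails 2 > 2. Replacing > with ≥ lowers the shortest qualifying duration from 3 to 2 inclusive days and reclassifies nothing else.

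**What one reclassified event would do.** These figures show sensitivity; they do not estimate the effect.

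- Per-injection rate: for a patient assumed to have all 52 weekly injections, each injection moved into A adds 100 × 1/52 = 1.9 percentage points to that patient's value.
- Patient incidence: this changes only for a patient who has no other qualifying ISR. With 20 patients per group (the sample size sections), one such patient moves the group's figure by 1/20 = 5.0 points. With 35 per group (70 randomized 1:1, the upper figure in Protocol 3.1 and SAP 1.1), it moves by 1/35 = 2.9 points.

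The number of such events or patients is not in the documents.

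**Where these events still appear.** SAP 3.7.2 defines a treatment-emergent event by its start or worsening relative to first dose, with no duration condition. A reaction resolving the next day therefore stays in the overall tables by preferred term, severity and relatedness, and in the listings.

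**The case against.** The strongest reply is that the words may mean elapsed time. A reaction that begins late one evening and clears the next morning touches two calendar dates but lasts only hours, and few would say it persisted for 2 days. If the intended meaning is resolution − start ≥ 2, words and formula agree at every gap in the table and nothing is lost. On that view, switching to ≥ 2 on an inclusive count would admit events that the authors meant to leave out.

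Part of this stands. The documents do not prove which meaning was intended, so the remedy must leave room for the elapsed-time rule. It does not remove the problem. The SAP nowhere says that duration is elapsed time, it adds one day in this very formula, and it counts treatment duration the same way. Read on the SAP's own convention, the sentence contradicts itself.

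It is also fair to say that the ISR outputs are additional to the general adverse event tables, and that the formula applies equally to both groups.

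**Conclusion.** The inconsistency is real and minor. As the formula is written, a documented reaction resolving the day after onset meets the stated wording and is left out of the three ISR-specific outputs. This rests on reading the words on the SAP's inclusive day count. The size of the effect cannot be derived, because no duration distribution is given. No efficacy result is affected.

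A reader might infer more than the documents support:

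- *That 2-day reactions vanish from safety reporting.* They remain in the general tables and listings.
- *That the loss is large because reactions are typically short.* Protocol 2.3.4 describes reactions as mild and self-resolving but says nothing about brief ones. Its description also concerns the subset already lasting 2 days or more, which it calls infrequent.
- *That the loss falls mostly on the active group.* No figure supports this; the same filter applies to both groups.
- *That the formula is what breaks comparison with the earlier rate.* Protocol 2.3.4 reports reactions "occurring on the day of injection and persisting for at least 2 days were infrequent (~15% of injections". That definition was limited to five symptoms with onset on the injection day, and its day count is not stated. The SAP accepts any matching term, any onset time and missing end dates. The two definitions differ whatever the inequality sign, and neither document plans the comparison.

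**What to change.** In SAP 3.7.2.1, state the duration rule once: AE resolution date − AE start date + 1 ≥ 2 days. This agrees with the section's own words and with the inclusive count used in SAP 3.7.5. Apply it to the ISR table, the patient incidence and the numerator of the per-injection rate. If at least 2 days of elapsed time was intended, keep the present cut but say so explicitly and reword the text to match.

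The cost is one symbol or one clause, with no new data. Under the first option the ISR set can only stay the same or grow, so the reported ISR rate may rise slightly.
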